## 1.3.2. Schedule of Activities for ED, Unscheduled Visits, and Post-Treatment Follow-up of Study J4H-MC-FVAA

Study J4H-MC-FVAA				Post-Treat	ment Follow-	·up	Comments
Visit number			801	802	803**	804**	For discontinuations that occur before Visit 802, see
	ED	UV*					the activities listed for ED in this table.
Weeks from randomization	_	_	14 or ED	16 or ED	20 or ED	24 or ED	* For unscheduled visits (UV), additional safety
			+	+	+	+	laboratory tests and procedures should be performed
			2 weeks	4 weeks	8 weeks	12 weeks	as needed.
			after last	after last	after last	after last	** V803 and V804 will only be performed if the
			dose	dose	dose	dose	PASI score from the previous visit (V802 and V803,
							respectively) is less than the baseline PASI score
							(see Section 7.2).
Visit interval tolerance (days)			±3	±3	±7	±7	
Fasting visit	X						Participants should not eat or drink anything
							except water for 12 hours before the visit.
Concomitant medications	X	X	X	X	X	X	
Adverse events (AEs)	X	X	X	X	X	X	Any events that occur after signing the informed
							consent are considered AEs as defined in
							Section 8.3.1.
							Additional data will be collected for infection-
							related AEs (Section 8.3.4).
Physical evaluation	<del></del>	Г	I	I	T	T	
Weight	X			X			
Vital signs	X	X	X	X	X	X	See Section 8.2.1.
Symptom-directed physical	X	X	X	X	X	X	As indicated based on participant status and
assessment							standard of care. May be performed by qualified
							personnel per local regulations. At least every 3
							months, assess for tuberculosis (TB) risk factors,
							and for signs and symptoms of active TB,
							including examination of peripheral lymph nodes;
							see Section 8.2.8.
12-lead ECG (central)	X						Collect ECG at least 30 minutes before blood
							samples for laboratory testing. ECG may be
							repeated at the investigator's discretion at any
							visit. See Section 8.2.4.

Study J4H-MC-FVAA				Post-Treat	ment Follow-	·up	Comments
Visit number			801	802	803**	804**	For discontinuations that occur before Visit 802, see
	ED	UV*					the activities listed for ED in this table.
Weeks from randomization			14 or ED	16 or ED	20 or ED	24 or ED	* For unscheduled visits (UV), additional safety
			+	+	+	+	laboratory tests and procedures should be performed
			2 weeks	4 weeks	8 weeks	12 weeks	as needed.
			after last	after last	after last	after last	** V803 and V804 will only be performed if the

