## 4. Study Design

## 4.1. Overall Design

Study FVAA is a Phase 2, randomized, double-blind, placebo-controlled study to evaluate the efficacy and safety of LY3972406 in adults with moderate-to-severe plaque psoriasis.

The study duration will be approximately 29 weeks over 3 study periods:

- **Screening**: occurs within 35 days before the planned randomization visit (baseline; Visit 2/Week 0)
- **Double-blind treatment period**: lasts for 12 weeks from baseline
- **Post-treatment follow-up**: lasts for up to 12 weeks after last treatment visit (or last dose for ED) (Visits 801-804)

**Note:** Visits 803 and 804 will only be performed if the PASI score from the previous visit (Visits 802 and 803, respectively) is less than the baseline PASI score (see Section 7.2 for details).

See SoA (Section 1.3) for additional details about the study visits and visit specific- assessments. The study schema is presented in Section 1.2.

The study will have 2 stages.

- In Stage 1, approximately participants will be randomly assigned to receive LY3972406 CCl or placebo CCl
- Stage 2 may be initiated at the sponsor's discretion post review of the interim analysis data from Stage 1, to collect additional safety and efficacy data at the collect dose level (see Section 9.4). If Stage 2 is implemented, approximately an additional participants will be enrolled. The participants will be randomly assigned to receive either

```
LY3972406 CCl , LY3972406 CCl or placebo CCl

OR

LY3972406 CCl or placebo CCl
```

For randomization stratification factors, see Section 6.3.

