# 7.2. Participant Discontinuation/Withdrawal from the Study

Discontinuation is expected to be uncommon.

A participant may withdraw from the study:

- at any time at the participant's own request for any reason or without providing any reason
- at the request of the participant's designee, for example, legal guardian
- at the discretion of the investigator for safety, behavioral, compliance, or administrative reasons
- if enrolled in any other clinical study involving an investigational product, or enrolled in any other type of medical research judged not to be scientifically or medically compatible with this study
- if the participant, for any reason, requires treatment with a therapeutic agent that is prohibited by the protocol and has been demonstrated to be effective for treatment of the study indication. In this case, discontinuation from the study occurs prior to introduction of the new agent.

In addition, discontinuation from the study will occur for the following reasons:

- At or after Visit 802, if the PASI score is greater than or equal to the baseline (Visit 2) PASI score.
- If an investigator, site personnel performing assessments, or participant is unblinded. In cases where there are ethical reasons to have the participant remain in the study, the investigator must obtain specific approval from the sponsor or designee for the participant to continue in the study.

At the time of discontinuing from the study, if possible, the participant will complete procedures for an ED visit and post-treatment follow-up, as shown in the SoA. If the participant has not already discontinued the study intervention, the participant will be permanently discontinued from the study intervention at the time of the decision to discontinue the study. Participants who discontinue the study at Week 16 onward due to a PASI score greater than or equal to the baseline PASI score are not required to complete an ED visit or additional post-treatment follow-up.

If the participant withdraws consent for disclosure of future information, the sponsor may retain and continue to use any data collected before such a withdrawal of consent. If a participant withdraws from the study, the participant may request destruction of any samples taken and not tested, and the investigator must document this in the site study records.

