# 8.3.1. Timing and Mechanism for Collecting Events

This table describes the timing, deadlines, and mechanism for collecting events.

Event	Collection Start	Collection Stop	Timing for Reporting to Sponsor or Designee	Mechanism for Reporting	Back-up Method of Reporting
Adverse Event					"
AE	Signing of the ICF	Participation in study has ended	As soon as possible upon site awareness	AE CRF	N/A
Serious Adverse	Event		,		
SAE and SAE updates – prior to start of study intervention and deemed reasonably possibly related to study procedures	Signing of the ICF	Start of intervention	Within 24 hours of awareness	SAE CRF	SAE paper form
SAE and SAE updates – after start of study intervention	Start of intervention	Participation in study has ended	Within 24 hours of awareness	SAE CRF	SAE paper form
SAE a – after participant's study participation has ended and the investigator becomes aware	After participant's study participation has ended	N/A	Promptly	SAE paper form	N/A
Pregnancy	Pregnancy				
Pregnancy in female participants and female partners of male participants	After the start of study intervention	At least 5 terminal half- lives after the last dose	Within 24 hours (see Section 8.3.2)	Pregnancy paper form	Pregnancy paper form

Event	Collection Start	Collection Stop	Timing for Reporting to Sponsor or Designee	Mechanism for Reporting	Back-up Method of Reporting
Product Complai	ints				
PC associated with an SAE or might have led to an SAE	Start of study intervention	End of study intervention	Within 24 hours of awareness	Product Complaint form	N/A
PC not associated with an SAE	Start of study intervention	End of study intervention	Within 1 business day of awareness	Product Complaint form	N/A
Updated PC information			As soon as possible upon site awareness	Originally completed Product Complaint form with all changes signed and dated by the investigator	N/A
PC (if investigator becomes aware)	Participation in study has ended	N/A	Promptly	Product Complaint form	

<sup>a SAEs should not be reported unless the investigator deems them to be possibly related to study treatment or study participation.

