#### Continuous and categorical data analyses

Continuous data will be summarized in terms of the mean, standard deviation, minimum, maximum, median, and number of observations. Categorical data will be summarized as frequency counts and percentages. Comparisons between each LY3972406 dose and placebo will be performed for all analyses in the treatment period with no adjustment for multiple comparisons.

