#### 4.7.2. Adverse Events

AEs are recorded in the electronic case report forms (eCRFs). Where changes in severity are recorded in the eCRF, each separate severity of the AE will be reported in the listings. Only the most severe will be used in the summary tables.

AEs will be coded according to the current version at the time of database lock of the Medical Dictionary for Regulatory Activities (MedDRA). The MedDRA lowest level term will be used in defining which events are treatment-emergent (TE). The severity of AEs is recorded as mild, moderate, or severe. The maximum severity for each lowest level term during the baseline period will be used as baseline. Baseline for the double-blind treatment period is defined as all preexisting conditions recorded at Visit 1 and any AEs recorded before the first dose of study intervention. The treatment period will be included as postbaseline for the analysis. For events with a missing severity during the baseline period, it will be treated as 'mild' in severity for determining treatment-emergence. Events with a missing severity during the postbaseline period will be treated as 'severe,' and treatment-emergence will be determined by comparing to baseline severity. For events occurring on the day of first taking study medication, the start times of the study treatment and AE will be used to determine whether the event was pre- versus posttreatment. If the start time for the AE is missing, it will be assumed to have started in the later period.

A TEAE is defined as an event that first occurred or worsened in severity after baseline and on or prior to the date of the last visit within the treatment period. For each event classification term, the number of participants experiencing a TEAE with that classification term will be tabulated. A follow-up emergent AE is defined as an event that first occurred or worsened in severity after Week 12 (Visit 9) or early discontinuation. For events that are gender-specific, the denominator and computation of the percentage will include participants only from the given gender. A preexisting condition is defined as a condition that starts before the participant has provided written informed consent and is ongoing at consent. A non-TEAE is defined as an AE that starts after informed consent but prior to the first dose. Further definitions and information for AEs can be found in FVAA Protocol in Section 8.3 and in Appendix 3, Section 10.3.

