In an overview table, the number and percentage of subjects who experienced a TEAE or SAE, died due to an AE, or discontinued from the study due to an AE will be summarized by treatment.

An overall summary of AEs will be provided for the population, treatment period, severity, and relationship to the study drug. The number of TEAEs, the number of participants experiencing a TEAE, and the percentage of participants experiencing a TEAE will be summarized by population, treatment, and MedDRA system organ class (SOC) and preferred term (PT). The MedDRA version is documented in the Data Management Plan. This includes the number and percentage of participants who experienced TEAEs, TEAEs by maximum severity, deaths, SAEs, TEAEs related to study intervention, and AEs leading to discontinuation of study intervention. The summary and frequency AE tables will be presented for all causalities and

those considered related to the study drug by the clinician. Any serious AEs will be listed. AEs by day of onset will be presented.

The number and percentage of patients with TEAEs will be summarized by treatment group in the 2 formats listed below:

- by MedDRA PT nested within a SOC, with SOCs ordered alphabetically and events ordered within each SOC by decreasing frequency in the treatment group, and
- by MedDRA PT with events ordered by decreasing frequency in the treatment group.

AEs leading to permanent discontinuation of study drug and AEs leading to temporary interruption of study drug will also be summarized by treatment group using MedDRA PT nested within SOC.

Follow-up emergent AEs, SAEs including deaths, and AEs leading to study discontinuation will be summarized for the posttreatment follow-up period.

Listings will be presented for all AEs, all SAEs, all AEs leading to death, all AEs leading to study drug temporary interruption, and all AEs leading to discontinuation from the study.

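### Follow-up adverse events are summarised over about 4, 8 or 12 weeks depending on PASI; without a common window or follow-up person-time, crude percentages are not comparable if retention differs by arm

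*SAP*

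**What the plan says.** **Length of follow-up.** Protocol 1.3.2 places Visits 801, 802, 803 and 804 at 2, 4, 8 and 12 weeks after the last dose. Protocol 4.1 makes the last two conditional: "Visits 803 and 804 will only be performed if the PASI score from the previous visit" is below the baseline score. Protocol 7.2 lists as a reason for discontinuation from the study: "At or after Visit 802, if the PASI score is greater than or equal to the baseline (Visit 2) PASI score". Participants who leave under that rule need no early discontinuation visit and no further follow-up.

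**Event collection.** Protocol 8.3.1 stops routine adverse event collection when "Participation in study has ended". For serious events after that point, its footnote says "SAEs should not be reported unless the investigator deems them to be possibly related to study treatment or study participation".

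**Analysis.** SAP 4.7.2 gives the definition: "A follow-up emergent AE is defined as an event that first occurred or worsened in severity after Week 12 (Visit 9) or early discontinuation". It sets no end to the window. The planned output is one sentence: "Follow-up emergent AEs, SAEs including deaths, and AEs leading to study discontinuation will be summarized for the posttreatment follow-up period". The general rule in SAP 4.1 is "Categorical data will be summarized as frequency counts and percentages". SAP 4.7.1 plans duration of exposure and patient-years for the double-blind period only. SAP 4.7 says that follow-up safety data are presented separately and that safety analyses use the safety set.

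**The concern.** A patient who leaves at Visit 802 can contribute events for about 4 weeks, and one who reaches Visit 804 for about 12. Who stays depends on PASI after randomisation, which treatment may influence. Pooling the three lengths into one percentage per arm mixes the event rate with the time observed. Late reports of possibly related serious events reach the sponsor only if the investigator happens to learn of them, so they do not even out the observation time.

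Protocol 4.2 gives the capture of additional safety signals as one purpose of this period, and these tables are where a reader would look for them. If more drug patients stay below baseline PASI, the drug could look worse than it is. If drug patients relapse faster, it could look better.

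**Working it through.** **The plan's own figure.** Screening of 35 days is 5 weeks, and 5 + 12 + 12 = 29 weeks, the study duration stated in Protocol 4.1. Follow-up visits at Weeks 14, 16, 20 and 24, less Week 12, fall at 2, 4, 8 and 12 weeks. The PASI rule acts at Visits 802 and 803, so the nominal lengths are 4, 8 or 12 weeks, before visit tolerances of ±3 or ±7 days and other withdrawals.

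**Inputs, all assumed.** The documents give no exit shares or event rates, and the arm sizes are redacted.
- s1 is the share below baseline PASI at Visit 802; s2 is the share of those still below it at Visit 803.
- R is the 12-week event risk (10%, 20% or 30%), the same in both arms, with constant weekly hazard h = −ln(1 − R)/12.
- n is 15 to 50 per arm. The only count left in the text is about 35 additional participants in total for Stage 2 (Protocol 2.3.3).

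**Formula.** The weights are 1 − s1 for 4 weeks, s1(1 − s2) for 8 weeks and s1·s2 for 12 weeks. The crude percentage is the weighted sum of 1 − exp(−hT).

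**Worked case (A, R = 20%).** h = 0.0186, so the risks by 4, 8 and 12 weeks are 7.17%, 13.82% and 20.00%.
- Drug, s1 = s2 = 0.90, weights 0.10, 0.09, 0.81: 0.717 + 1.244 + 16.200 = 18.16%.
- Placebo, s1 = 0.60 and s2 = 0.80, weights 0.40, 0.12, 0.48: 2.867 + 1.659 + 9.600 = 14.13%.

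| Scenario (drug s1, s2 vs placebo) | R = 10% | R = 20% | R = 30% | Ratio |
|---|---|---|---|---|
| A: more drug patients stay (0.90, 0.90 vs 0.60, 0.80) | 9.1 vs 7.0 | 18.2 vs 14.1 | 27.3 vs 21.4 | about 1.3 |
| B: similar retention (0.85, 0.85 vs 0.75, 0.85) | 8.6 vs 8.0 | 17.3 vs 16.1 | 26.1 vs 24.3 | 1.07–1.08 |
| C: equal retention | equal | equal | equal | 1.00 |
| D: faster relapse on drug (0.60, 0.70 vs 0.80, 0.90) | 6.8 vs 8.4 | 13.8 vs 16.9 | 20.9 vs 25.5 | 0.81–0.82 |

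Mean follow-up is 10.8 against 8.3 weeks in A and 8.1 against 10.1 weeks in D.

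**Size in patients.** n times the difference gives 0.3 to 3.0 patients in A, 0.1 to 0.9 in B and −0.2 to −2.3 in D. At R = 20%, the 4.0-point gap in A has a standard error of 13.4 points (n = 15) to 7.3 points (n = 50). In A, B and D the gap stays below one standard error at every R and n used.

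**Common window.** 1 − exp(−4h) is 3.5%, 7.2% and 11.2% in both arms, whatever happens after Visit 802. It holds 38% to 54% of the patients expected to have an event over the whole period.

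**Exposure-adjusted rates.** Suppose the hazard falls, from 0.03 per week up to week 4 to 0.015 afterwards, equally in both arms. In A the crude ratio is 1.19 (19.9% vs 16.7%), but the rate ratio is 0.93 (1.09 vs 1.18 per patient-year). In D they are 0.87 and 1.07. The rate errs in the opposite direction, while a full 4-week window gives 11.3% in both arms.

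**The case against.** The strongest reply is that these are descriptive tables in a small Phase 2 study. SAP 4.1 and 4.7 confine planned comparisons to the treatment period, and no hypothesis uses follow-up events. The SAP sentence says only that events will be summarised; percentages come from the general rule. All of that stands, and it limits the weight of the point.

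A reader might also infer that the planned output hides unequal follow-up. It does not, quite. Laboratory tests and vital signs are scheduled at Visits 801 to 804. SAP 4.7.3 summarises them at each visit, and SAP 4.1 includes the number of observations. These tables should show roughly how many remain per arm, and with the adverse event listings a reviewer could rebuild a common window by hand. Nor can one say that the day-of-onset display in SAP 4.7.2 lacks numbers at risk: the SAP does not say whether it covers follow-up or shows them.

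A third reply is that cutting at Visit 802 does not equalise everyone. Visit 802 is timed from the last dose, so it falls less than 4 weeks after an early discontinuation visit that is itself later than the last dose. Some participants also withdraw sooner. This is correct, and the remedy has to allow for it.

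None of these replies supplies a display in which the arms are observed for a common time.

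**Conclusion.** The point holds as a conditional reporting weakness. The follow-up summary pools outcome-dependent windows of about 4, 8 and 12 weeks, and the SAP plans neither a common window nor follow-up person-time. If retention below baseline PASI differs by arm, crude percentages differ at equal event rates: by a factor of about 1.3 in scenario A and about 0.8 in D. If retention is equal, nothing is distorted. These sizes rest on assumed retention, an assumed constant hazard and assumed arm sizes.

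The documents do not support the stronger reading that the follow-up tables will be biased against the drug, or for it. Protocol 2.3.2 says there are no clinical efficacy data yet, so neither a retention difference nor its direction is known. The treatment-emergent tables and the efficacy analyses are unaffected. The change is worth making because it is cheap, not because a main conclusion is at risk.

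**What to change.** In SAP 4.7.2, keep the whole-period summary and add by arm:

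1. The number and percentage of participants with follow-up emergent adverse events, and with serious ones, in a fixed window of about 4 weeks that closes no later than the scheduled Visit 802. State one starting point for all participants, for example days since Visit 9 or early discontinuation. Show the number still under observation when the window closes, so that withdrawals before Visit 802 are visible.
2. Follow-up duration (person-time), beside the whole-period summary.

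Exposure-adjusted rates are an optional supplement, with the caveat that they assume a roughly constant hazard.

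Two clarifications would help. State whether the denominator is the whole safety set named in SAP 4.7 or those who entered follow-up, since the Follow-up set in SAP 3 is tied to no table. Show exits under the PASI rule as their own reason in the SAP 4.2 disposition summary.

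The cost is SAP wording and one or two extra tables from data already collected. The fixed window leaves out later events, which is why the whole-period summary stays. No visit rule or clinical rule changes.

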## 4.7.3. Vital Signs, Laboratory Analytes and ECGs

Vital signs include systolic blood pressure, diastolic blood pressure, pulse, weight, and body mass index. Original-scale data will be analyzed. When these parameters are analyzed as continuous numerical variables, unplanned measurements will be excluded. When these parameters are analyzed as categorical outcomes, TE abnormalities, or both, planned and unplanned measurements will be included. The planned analyses described for the laboratory analytes in this section below will be used to analyze the vital signs, except for the inclusion of a threshold for change in addition to a limit for the definition of TE. Table FVAA 4.1 defines the low and high baseline values as well as the criteria used to define TE based on postbaseline values.

Table FVAA 4.1 Categorical Criteria for Abnormal Treatment-Emergent Blood Pressure and Pulse Measurement, and Categorical Criteria for Weight Changes for Adults

Parameter	Low	High
Systolic BP (mmHg) (Supine or sitting – forearm at heart level)	≤90 and decrease from baseline ≥20	≥140 and increase from baseline ≥20
Diastolic BP (mm Hg) (Supine or sitting – forearm at heart level)	≤50 and decrease from baseline ≥10	≥90 and increase from baseline ≥10
Pulse (bpm) (Supine or sitting)	<50 and decrease from baseline ≥15	100 and increase from baseline ≥15
Weight (kg) (Consistent clothing and timing in relationship to meals and voiding)	(Loss) decrease ≥7%	(Gain) increase ≥7%

Abbreviation: BP = blood pressure.

Laboratory analytes and vital signs will be summarized by population at each visit. For continuous data, change from baseline will also be summarized, where baseline is defined as the Visit 2 assessment for laboratory analytes and the Day 1 predose assessment for vital signs. Additionally, laboratory analytes data outside the reference ranges will be listed and flagged on individual participant data listings.

The ECG data will be obtained directly from the 12-lead ECG traces. These data include the PR, QT, QT interval corrected using Bazett's formula intervals, QRS duration, and heart rate (HR). In addition, QT interval corrected using Fridericia's formula (QTcF) will be calculated as follows:

$$QTcF = \frac{QT}{\sqrt[3]{60/HR}}$$

ECG data will be summarized at each timepoint for each treatment arm together with changes from baseline, where baseline is defined as the Day 1 predose triplicate assessment.

A table providing the counts and percentages of subjects with greater than 30 and greater than 60 maximum increase in QTcF intervals, as well as the frequency and percentages of maximum QTcF intervals greater than 450, greater than 480, and greater than 500, will be provided for each treatment arm.

